## **9.0 TRIAL PROCEDURES**

### **9.1 Trial Procedures**

The Trial Flow Chart - Section 8.0 summarizes the trial procedures to be performed at each visit. Individual trial procedures are described in detail below. Study treatment is expected up to two years. It may be necessary to perform these procedures at unscheduled time points if deemed clinically necessary by the investigator.

Furthermore, additional evaluations/testing may be deemed necessary by the Sponsor and/or Merck for reasons related to subject safety. In some cases, such evaluation/testing may be potentially sensitive in nature (e.g., HIV, Hepatitis C, etc.), and thus local regulations may require that additional informed consent be obtained from the subject. In these cases, such evaluations/testing will be performed in accordance with those regulations.

Data collection is the responsibility of the clinical trial staff at the site under the supervision of the site investigator. The investigator is responsible for ensuring the accuracy, completeness, legibility, and timeliness of the data reported.

All source documents should be completed in a neat, legible manner to ensure accurate interpretation of data.

Clinical data (including adverse events (AEs), concomitant medications, and expected adverse reactions data) and clinical laboratory data will be entered into Forte EDC, a password-protected data capture system provided by the UVA Coordinating Center / GTcLC. Clinical data will be entered directly from the source documents.

#### **9.1.1 Administrative Procedures**

##### **9.1.1.1 Informed Consent**

The Investigator must obtain documented consent from each potential subject prior to participating in a clinical trial.

##### **9.1.1.2 General Informed Consent**

Consent must be documented by the subject's dated signature or by the subject's legally acceptable representative's dated signature on a consent form along with the dated signature of the person conducting the consent discussion.

A copy of the signed and dated consent form should be given to the subject before participation in the trial.

The initial informed consent form, any subsequent revised written informed consent form and any written information provided to the subject must receive the IRB/ERC's approval/favorable opinion in advance of use. The subject or his/her legally acceptable representative should be informed in a timely manner if new information becomes available that may be relevant to the subject's willingness to continue participation in the trial. The communication of this information will be provided and documented via a revised consent form or addendum to the original consent form that captures the subject's dated signature or by the subject's legally acceptable representative's dated signature.

Specifics about a trial and the trial population will be added to the consent form template at the protocol level.

The informed consent will adhere to IRB/ERC requirements, applicable laws and regulations and Sponsor requirements.

### **9.1.2 Inclusion/Exclusion Criteria**

All inclusion and exclusion criteria will be reviewed by the investigator or qualified designee to ensure that the subject qualifies for the trial.

### **9.1.3 Medical History**

A medical history will be obtained by the investigator or qualified designee. Medical history will include all active conditions, and any condition diagnosed within the prior 10 years that are considered to be clinically significant by the Investigator. Details regarding the disease for which the subject has enrolled in this study will be recorded separately and not listed as medical history.

### **9.1.4 Prior and Concomitant Medications Review**

#### **9.1.4.1 Prior Medications**

The investigator or qualified designee will review prior medication use, including any protocol-specified washout requirement, and record prior medication taken by the subject within 28 days before starting the trial. Treatment for the disease for which the subject has enrolled in this study will be recorded separately and not listed as a prior medication.

#### **9.1.4.2 Concomitant Medications**

The investigator or qualified designee will record medication, if any, taken by the subject during the trial. All medications related to reportable SAEs and ECIs should be recorded as defined in Section 9.2.

### **9.1.5 Disease Details and Treatments**

#### **Disease Details**

The investigator or qualified designee will obtain prior and current details regarding disease status.

#### **Prior Treatment Details**

The investigator or qualified designee will review all prior cancer treatments including systemic treatments, radiation and surgeries.

#### **Subsequent Anti-Cancer Therapy Status**

The investigator or qualified designee will review all new anti-neoplastic therapy initiated after the last dose of trial treatment. If a subject initiates a new anti-cancer therapy within 30 days after the last dose of trial treatment, the 30-day Safety Follow-up visit must occur before the first dose of the new therapy. Once new anti-cancer therapy has been initiated the subject will move into survival follow-up.

### **9.1.6 Clinical Procedures/Assessments**

#### **9.1.6.1 Adverse Event (AE) Monitoring**

The investigator or qualified designee will assess each subject to evaluate for potential new or worsening AEs as specified in the Trial Flow Chart and more frequently if clinically indicated. Adverse experiences will be graded and recorded throughout the study and during the follow-up period according to NCI CTCAE Version 5.0 (see [Section 11.3](#)). Toxicities will be characterized in terms regarding seriousness, causality, toxicity grading, and action taken with regard to trial treatment.

Please refer to [section 9.2](#) for detailed information regarding the assessment and recording of AEs.

#### **9.1.6.2 Physical Exam**

The investigator or qualified designee will perform a physical exams according to standard clinical care during the study period. Clinically significant abnormal findings at screening/baseline should be recorded as medical history.

#### **9.1.6.3 Vital Signs**

The investigator or qualified designee will take vital signs at screening, prior to the administration of each dose of trial treatment and at treatment discontinuation as specified in the Trial Flow Chart (Section 8.0). Vital signs should include temperature, pulse, respiratory rate, weight and blood pressure. Height will be measured at screening only.

#### **9.1.6.4 Eastern Cooperative Oncology Group (ECOG) Performance Scale**

The investigator or qualified designee will assess ECOG status as outlined in the study flow chart (see Section 8.0).

#### **9.1.6.5 Tumor Imaging and Assessment of Disease**

The primary objectives are to evaluate the safety, tolerability, and efficacy of the study drugs. All patients will be assessed by standard criteria for clinical response. Patients with measurable disease will be assessed by standard criteria. For patients with PTCL, response will be evaluated with physical exam, computerized tomography (CT) and tissue biopsies as defined by the lymphoma response to immunomodulatory therapy criteria or LYRIC (Cheson *et al.*, 2016). Positron emission tomography / computerized tomography (PET/CT) will be utilized if available (optional).

For patients with CTCL and PTCL with skin involvement, we recommend skin assessments using mSWAT, preferably by the same investigator at all times (to limit inter-observer variability) during the screening period and during the treatment period as defined in Study Flow Chart. Please find mSWAT worksheet in [section 11.2](#). Additional assessments will be performed as clinically indicated at investigator discretion.

In particular, we strongly recommend standardized photographs of the skin involvement to document the appearance of skin lesions at baseline (screening or Cycle 1 day 1) and as defined in Study Flow Chart. Blood involvement assessments will be performed for only CTCL patients at the same time as the skin assessments.

Evaluable for objective response. Patients who have received at least one cycle of therapy will be considered evaluable for response. These patients will have their response classified according to the definitions stated below. Patients who exhibit objective disease progression prior to the end of cycle 1 will also be considered.

The following disease parameters will be assessed.

Measurable disease. Measurable lesions are defined as those that can be accurately measured in two dimensions (longest diameter to be recorded) as  $\geq 20$  mm with conventional techniques (PET/CT, MRI, x-ray) or as  $\geq 10$  mm with spiral CT scan. All tumor measurements will be recorded in millimeters (or decimal fractions of centimeters). Tumor volume will be recorded as the sum of the product of the diameters (SPD) of the largest predominant target lesions. FDG avidity is based on comparison with background tissues. There is no specific SUV value that is considered a cut-off.

Non-measurable disease (evaluable disease). All other lesions (or sites of disease), including small lesions ( $<10$  mm using spiral CT scan), are considered non-measurable disease. Bone lesions, leptomeningeal disease, ascites, pleural/pericardial effusions, lymphangitis cutis/pulmonitis,

inflammatory breast disease, abdominal masses (not followed by CT or MRI), and cystic lesions are all non-measurable.

Target lesions. All measurable lesions up to a maximum of 6 lesions total, representative of all involved organs, should be identified as target lesions and recorded and measured at baseline. Target lesions should be selected on the basis of their SUV avidity (High SUV lesions will be prioritized, even if not the largest lesions) and size (lesions with the largest SPD diameter) and their suitability for accurate repeated measurements (either by imaging techniques or clinically). An SPD for all target lesions will be calculated and reported as the baseline sum SPD. The baseline sum SPD will be used as reference by which to characterize the objective tumor response based on CT criteria.

Non-target lesions. All other lesions (or sites of disease) including any measurable lesions over and above the 6 target lesions should be identified as non-target lesions and should also be recorded at baseline. Measurements of these lesions are not required, but the presence or absence of each should be noted throughout follow-up.

The guidelines to assess response will be based on the Olsen (Olsen et al., 2011) and the Lymphoma Response to Immunomodulatory Therapy Criteria or LYRIC (Cheson et al., 2016).

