## 3.0 OBJECTIVES & HYPOTHESIS

### 3.1 Primary Objectives & Hypothesis

- Determine the maximum tolerated dose (MTD), recommended phase 2 dose (RP2D) and dose limiting toxicity (DLT) of the combinations of pembrolizumab and pralatrexate (Arm A), pralatrexate, decitabine and pembrolizumab (Arm B), and decitabine and pembrolizumab (Arm C) in patients with relapsed/refractory PTCL and CTCL.
- Evaluate the safety and toxicity of the combination of pembrolizumab and pralatrexate (Arm A), pralatrexate, decitabine and pembrolizumab (Arm B), and decitabine and pembrolizumab (Arm C) in patients with relapsed/refractory PTCL and CTCL.
- Evaluate the efficacy, as determined by the ORR (complete + partial response), of the combination of pembrolizumab and pralatrexate (Arm A), pralatrexate, decitabine and pembrolizumab (Arm B), and decitabine and pembrolizumab (Arm C) in patients with relapsed/refractory PTCL and CTCL.

**Hypothesis:** If pralatrexate and/or decitabine functions in an immunomodulatory fashion then priming and modulating the malignant cells and the microenvironment will enhance the antitumor activity of pembrolizumab in patients with PTCLs and CTCLs.

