### 7.2 Dose Delays

These dose delays apply to all drugs and patients on all study arms. Additional delays may apply for specific drugs (see sections 7.3.1 and 7.3.2 below).

- Study drugs can be administered within 48 hours of their scheduled time.
- Study drugs will be held for DLT and any grade 3/4 toxicity not addressed in [section 5.3](#) until the AE returns to grade  $\leq 2$  unless otherwise specified in the sections below.
- If the interruption lasts for more than 14 days, study treatment will be discontinued.

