## **10.0 STATISTICAL CONSIDERATIONS**

### **10.1 Study Design**

This is a Phase Ib study evaluating the safety and efficacy of pembrolizumab combined with pralatrexate (Arm A) or decitabine (Arm C) or decitabine and pralatrexate (Arm B) in patients with peripheral T-cell lymphoma (PTCL) and cutaneous T-cell lymphoma (CTCL). In all arms, toxicity will be assessed according to the NCI Common Toxicity Criteria for Adverse Events (CTCAE), version 5.0. Dose-limiting toxicity (DLT) is a binary outcome (yes/no) and will be determined by adverse events occurring during the first cycle of treatment (see Section 5.3 for DLT definition). In all arms, the maximum tolerated dose (MTD) is defined as the dose combination with a DLT rate closest to the target DLT rate of 25%. The study will accrue participants in cohorts of size 1 in all arms. After accrual of a participant to an arm, the accumulating DLT data will be used to update the model-based estimated DLT

probabilities for each dose level. These estimates will then be used to update the recommended dose level for the next participant accrued to that arm of the study.

Arms A and C:

The primary objectives of Arms A and C is to determine the MTD, defined by acceptable toxicity, of decitabine (Arm C) or pralatrexate (Arm A) (plus a fixed dose of pembrolizumab) from among the 3 study dose levels in the following tables, and to evaluate efficacy, as determined by overall response rate, at the estimated MTD.

Arm A		
Dose Level	Pralatrexate	Pembrolizumab*
Level 1 (start)	30 mg/m  day 1, 8, 15	200 mg day 1
Level -1	30 mg/m  day 1, 15	200 mg day 1
Level -2	20 mg/m  day 1, 15	200 mg day 1

Arm C		
Dose Level	Decitabine	Pembrolizumab*
Level 1 (start)	20 mg/m  day 1->5	200 mg day 8
Level -1	20 mg/m  day 1->3	200 mg day 8
Level -2	10 mg/m  day 1->3	200 mg day 8

Based on the accumulated data from the previous 5 subjects (1 observed DLT) accrued to Arm A, the first eligible subject in Arm A will be entered onto Level 1. Based upon the accumulated data from the previous 4 subjects (2 observed DLTs) accrued to Arm C, the first eligible subject in Arm C will be entered onto Level -1.

Arm B:

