### 10.4 Sample size and accrual

A maximum target accrual of 5 additional eligible participants is planned in Arm A (total accrual n=10) and 6 additional eligible participants in Arm C (total accrual n=10). A maximum target accrual of 26 additional eligible participants is planned in Arm B (total accrual n=30), but simulation results below indicate that the average estimated

sample size needed to complete accrual to Arm B is between 3.5 (total accrual n=7.5) and 11.3 (total accrual n=15.3) additional participants. Maximum total sample size for all arms is estimated to be approximately 23 additional participants (total accrual n=36). For estimation of ORR at the MTD, a sample size of 7 at the MTD produces a two-sided 80% binomial confidence interval with a width equal to 0.556 when the sample proportion is 0.5. Additional subjects will be enrolled to replace any subjects who are enrolled, but do not receive treatment. Accrual is estimated at 2 participants per month. Adjusting for an approximate 5% drop-out/ineligibility rate, maximum target accrual should not exceed 38 participants.

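### The only response-evaluable set in the protocol leaves out treated participants who stop in cycle 1 without progression, conflicts with the n = 7 basis in Section 10.4, and would tend to bias ORR upward if used as the denominator.

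*Protocol*

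**What the plan says.** Section 3.1 lists ORR, as complete plus partial response, among the primary objectives for each arm. Section 10.1 repeats the aim, for Arms A and C and again for Arm B: "to evaluate efficacy, as determined by overall response rate, at the estimated MTD".

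Section 9.1.6.5 says who counts for response: "Patients who have received at least one cycle of therapy will be considered evaluable for response". One group is added: "Patients who exhibit objective disease progression prior to the end of cycle 1 will also be considered". The same section says earlier that all patients will be assessed for clinical response, but that sentence sets no analysis population.

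Section 10.4 gives the precision for ORR: "a sample size of 7 at the MTD produces a two-sided 80% binomial confidence interval with a width equal to 0.556", for a sample proportion of 0.5. It provides replacements only for participants who enrol and are never treated.

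Section 10.6 gives 90% Agresti-Coull intervals for dichotomous endpoints, overall response included. It does not say which participants form the denominator.

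**The concern.** A one-cycle rule removes early failures from a response analysis. The protocol repairs this for early progression but not for the other ways of failing early: stopping for toxicity, death without documented progression, or withdrawal. Participants removed in these ways will seldom have a recorded response, so leaving them out tends to raise the rate.

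The timing makes this matter. Section 10.1 says that DLT "will be determined by adverse events occurring during the first cycle of treatment", so evaluability turns on the same window in which DLTs are counted, and the MTD is the dose whose DLT rate is closest to 25%. The protocol also provides routes from toxicity to stopping. Section 7.2 states: "If the interruption lasts for more than 14 days, study treatment will be discontinued". Section 7.10 ends all study treatment when one drug of the combination is discontinued, or held beyond two weeks, for an adverse event. Table 10 in Section 7.3.1 requires permanent discontinuation for several immune-related events.

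At stake is the estimate for a primary objective, in groups small enough that one or two exclusions change the reported figure.

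**Working it through.** **Inputs.** Seven participants at the MTD, an 80% interval width of 0.556 and replacement of untreated participants only (Section 10.4). 90% Agresti-Coull intervals for response (Section 10.6). A 25% target DLT rate (Section 10.1). First on-study imaging after cycle 2 (Section 8.0, footnote 4 of each flow chart). Assumptions, because the documents give no figure: 3 responders, and d treated non-responders excluded.

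**Step 1. Reproduce the stated width.** The Clopper-Pearson limits at 80% are the 0.10 quantile of Beta(x, n−x+1) and the 0.90 quantile of Beta(x+1, n−x). With n = 7 and x = 3.5 they are 0.222 and 0.778, a width of 0.5559, which matches 0.556. The figure therefore needs all 7 in the denominator. At the same proportion of 0.5, the width is 0.598 with 6 evaluable and 0.650 with 5.

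**Step 2. Effect on the estimate.** The all-treated rate is r/N and the evaluable-only rate is r/(N−d). The Agresti-Coull interval uses k = 1.645, ñ = n + k², p̃ = (x + k²/2)/ñ and limits p̃ ± k√(p̃(1−p̃)/ñ). For 3/7, ñ = 9.706 and p̃ = 4.353/9.706 = 0.448, which gives 0.19 to 0.71.

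| Treated | Responders | Excluded (d) | ORR | 90% Agresti-Coull |
|---|---|---|---|---|
| 7 | 3 | 0 | 3/7 = 42.9% | 19–71% |
| 7 | 3 | 1 | 3/6 = 50.0% | 22–78% |
| 7 | 3 | 2 | 3/5 = 60.0% | 27–86% |
| 10 | 3 | 0 | 3/10 = 30.0% | 12–56% |
| 10 | 3 | 1 | 3/9 = 33.3% | 14–60% |
| 10 | 3 | 2 | 3/8 = 37.5% | 16–65% |

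**Step 3. General form.** If a proportion s of those treated is excluded and all of them are non-responders, ORR is multiplied by 1/(1−s): 1.05 at 5%, 1.11 at 10% and 1.33 at 25%. The last is the upper case, in which the DLT rate is on target and every DLT ends treatment within cycle 1.

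**Step 4. Link to the DLT target.** With 7 participants at a 25% rate, 7 × 0.25 = 1.75 DLTs are expected, and the chance of at least one is 1 − 0.75⁷ = 0.867. These are counts of DLTs, not of participants who stop. They cap the toxicity part of s at the target rate and do not estimate it. Excluding 2 of 7 (29%) lies slightly above that upper case, and 1 of 7 (14%) lies inside it.

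**The case against.** **No sentence makes this set the ORR denominator.** Section 9.1.6.5 is a procedures section, and the 7 in Section 10.4 matches the count treated at a dose in the stopping rules of Section 10.3, which points to an all-treated reading. A separate analysis plan might also settle the matter. The first part stands: a reader might infer that the protocol fixes ORR on the evaluable set, and it does not say so. What remains is that the protocol defines one response population, computes precision on another basis, and does not say which governs.

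**Excluded participants could respond.** A reader might infer that none of them can be a responder. Section 7.10 does not support this, because those who discontinue for reasons other than progression are followed for disease status. With the first scheduled scan after cycle 2, a recorded response is unlikely but possible.

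**A DLT is not a stop in cycle 1.** A reader might carry the 25% target straight into a 25% loss. Under Section 7.2 a DLT generally leads to a hold, with discontinuation if the interruption exceeds 14 days. Under Section 5.3, failing the blood parameters for cycle 2 day 1 is itself a DLT, and that participant has reached the end of cycle 1. In Arms B and C the last cycle-1 doses fall on day 15 and day 8, so a later DLT may strike someone who has arguably received the cycle. The protocol does not define a received cycle. All of this stands and limits the size.

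**ORR is descriptive.** No test, threshold or comparison between arms rests on it, the intervals overlap widely, and toxicity is tabulated by dose level and arm. This lowers the consequence, but ORR is still a primary objective.

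**Conclusion.** The point holds as a conflict within the protocol, with a probable direction of bias. Section 9.1.6.5 leaves out some treated early failures, while the precision in Section 10.4 holds only if no treated participant is lost. If the evaluable set is used, ORR tends to be too high, provided those excluded respond less often than those kept.

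The size cannot be fixed from the documents. For 3 responders among 7 treated, the assumed range is 43% with none excluded, 50% with one and 60% with two. As a multiplier it is 1.05 to 1.11 at exclusion proportions of 5% to 10%, and 1.33 in the upper case of 25%. The planned 80% interval width of 0.556 becomes 0.598 or 0.650 with one or two lost. The change should be made, but the documents do not show that the reported ORR will be inflated by any particular amount.

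**What to change.** State in Sections 9.1.6.5 and 10.6 that the denominator for the primary ORR is every participant who received any protocol treatment at the MTD, and that those without a response assessment count as non-responders. Keep the one-cycle set as a supportive analysis, and say there what receiving a cycle means.

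This agrees with the n = 7 basis and the replacement rule in Section 10.4, so the stated width of 0.556 can stay. The cost is about a sentence in each section. No new data are needed, and the reported ORR may be lower.

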#### **9.1.7 Laboratory Procedures/Assessments**

Details regarding specific laboratory procedures/assessments to be performed in this trial are provided below. Laboratory tests for hematology, chemistry, urinalysis, and others are specified in Table 15.

Table 15: Laboratory Tests

Hematology	Chemistry	Urinalysis	Other
Hematocrit	Albumin	Blood	Serum $\beta$ -human chorionic gonadotropin† ( $\beta$ -hCG)†
Hemoglobin	Alkaline phosphatase	Glucose	
Platelet count	Alanine aminotransferase (ALT)	Protein	PT (INR)
WBC (total and differential)	Aspartate aminotransferase (AST)	Specific gravity	aPTT
Red Blood Cell Count	Lactate dehydrogenase (LDH)	Microscopic exam ( If abnormal )	Total triiodothyronine (T3)
Absolute Neutrophil Count	Carbon Dioxide ‡	results are noted	Free tyroxine (T4)
Absolute Lymphocyte Count	( $CO_2$ or bio carbonate)	Urine pregnancy test †	Thyroid stimulating hormone (TSH)
	Uric Acid		PK
	Calcium		EBV PCR
	Chloride		Blood for correlative studies
	Glucose		
	Phosphorus		
	Potassium		
	Sodium		
	Magnesium		
	Total Bilirubin		
	Direct Bilirubin ( If total bilirubin is elevated above the upper limit of normal )		
	Total protein		
	Blood Urea Nitrogen		
	Creatinine		

† Perform on women of childbearing potential only. If urine pregnancy results cannot be confirmed as negative, a serum pregnancy test will be required.

‡ If considered standard of care in your region.

Laboratory test before every day 1 of treatment, except cycle 1 day 1, should be performed within 72 hours prior to study treatment.

For cycle 1 day 1 laboratory screening tests can be considered valid for treatment on cycle 1 day 1 as long as they are performed within the screening laboratory test window (10 days). After Cycle 1, pre-dose laboratory procedures can be conducted up to 72 hours prior to dosing. Results must be reviewed by the investigator or qualified designee and found to be acceptable prior to each dose of trial treatment.

